15c. Intention to treat and missing data. Analyses will be performed in accordance with the intent-to-treat principle, meaning that all participants who return at least one follow-up biosample will be included in analyses, regardless of adherence or other characteristics observed after randomization. Multiple imputation for study participants missing year 5 eGFR will be conducted using chained equations, utilizing baseline data as well as eGFR and urine ACR data available at year 2.¹⁸⁰ Results from 10 imputation datasets will be combined using Rubin's rules.¹⁸¹

15d. Treatment interaction. We will assess for interaction of the study interventions (vitamin D and omega-3 fatty acids) for the primary outcome.¹⁸² We will use a linear mixed model to test for interaction:¹⁸³

$$\text{Equation 1: } eGFR_{ij} = \beta_0 + \beta_1(\text{vitamin D}_i) + \beta_2(\omega-3 \text{ FA}_i) + \beta_3(\text{vitamin D}_i \times \omega-3 \text{ FA}_i) + \beta_4(\text{vitamin D}_i \times t_{ij}) + \beta_5(\omega-3 \text{ FA}_i \times t_{ij}) + \beta_6(\text{vitamin D}_i \times \omega-3 \text{ FA}_i \times t_{ij}) + a_i + e_{ij}$$

where i denotes the i th participant and $j=0,2,5$ represents the time period, t is time modeled categorically, (vitamin D) is active vitamin D treatment assignment (yes/no), (ω -3 FA) is active omega-3 treatment assignment (yes/no), a_i is a random effect for patient, and e is statistical error. A p value < 0.05 for β_6 will be interpreted as evidence of interaction. If we observe interaction, all analyses will separately compare each of the 3 active treatment groups to the treatment group which receives (placebo + placebo). If there is no evidence of interaction, as hypothesized, all participants assigned to any active vitamin D will be compared to all participants assigned to placebo vitamin D, and all participants assigned to any active omega-3 fatty acids will be compared to all participants assigned to placebo omega-3 fatty acids.

15e. Hypothesis testing. The primary outcome is a continuous variable which will be tested using a linear mixed model with random intercepts. To test whether the change in eGFR differs by vitamin D treatment assignment in the absence of interaction with omega-3 fatty acids, we will test:

$$\text{Equation 2: } eGFR_{ij} = \beta_0 + \beta_1(\text{vitamin D}_i) + \beta_2(t_{ij}) + \beta_3(\text{vitamin D}_i \times t_{ij}) + a_i + e_{ij}$$

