where β_3 represents the difference in change in eGFR over time, comparing those on active vitamin D₃ to those on placebo. The corresponding 95% confidence interval and p-value reflect statistical significance of the treatment effect. We will use this model to describe treatment effects at years 2 and 5 but reserve statistical inference for year 5 alone. Corresponding equations will test the effect of omega-3 treatment assignment on eGFR as well as treatment effects on urine ACR, analyzed as a log-transformed continuous variable. The relatively large sample size makes it likely that few or no substantial differences in baseline characteristics will be present. In the event that any baseline characteristics are not balanced between treatment groups, sensitivity analyses will add to the model additional terms for such baseline characteristics. If we observe differences by treatment group in medication use (e.g. glucose-lowering or antihypertensive medications) or

laboratory covariates (e.g. hemoglobin A1c, CRP, IL-6) over follow-up, we will explore whether such differences may mediate or attenuate treatment effects by adding terms for these covariates to the model. We will assess secondary categorical outcomes using discrete Cox proportional hazards models.¹⁸⁴

15f. Subgroup analyses. For the vitamin D intervention, prespecified subgroup analyses will be based on baseline total and bioavailable serum 25(OH)D concentrations, urine ACR, and eGFR as well as race/ethnicity: we hypothesize that effects will be greater among participants who have low 25(OH)D at baseline, who have DKD (urine ACR ≥ 30 mg/g or eGFR < 60 mL/min/m 2) at baseline, or are Caucasian.^{185,186} For the omega-3 fatty acid intervention, prespecified subgroup analyses will be based on baseline levels of EPA+DHA and hsCRP: we hypothesize that effects will be greater among participants who low levels of EPA+DHA or high concentrations of hsCRP at baseline. Effect modification will be tested by including interaction terms of treatment assignment with subgroup in linear mixed models (Equation 2).

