15g. Exploratory adherence and efficacy analyses. All primary analyses will be performed according to the intent-to-treat principle (Section D15e). We plan secondary, *exploratory* analyses for the following limited purposes: (a) to evaluate whether null findings, if observed, are robust (i.e. not readily attributable to defects in the study interventions or their administration); and/or (b) to more comprehensively evaluate the potential range of treatment effects, if treatment effects are observed. We understand and acknowledge that these analyses, which are based on data collected after randomization, may introduce bias into study results. We will therefore use caution to limit their interpretation. We will first repeat analyses among the subset of participants who report continuous adherence to $\geq 80\%$ of study medications. In addition, we will assess whether changes in 25(OH)D and EPA+DHA levels are associated with changes in urine ACR and eGFR. For the latter analyses, change in 25(OH)D concentrations or change in EPA+DHA concentration (continuous variables) will replace treatment assignment in linear mixed models.

D16. Power. We calculated power using simulation (2000 replications) and the following assumptions: independent and equal allocation of participants to each treatment; 1,058 participants (80%) contributing at least one follow-up blood sample (as supported in Section D10); variation in eGFR and its change over time as observed in the preliminary data from our study population (Section D12); and no interaction between treatments. With these assumptions, we have 80% power (two-sided alpha=0.05) to detect a 2.3 mL/min/1.73m 2 difference in eGFR at year 5, comparing each active treatment to placebo. Power for alternative effect sizes is shown in Figure 7. We do not present power for secondary outcomes because the incidence of these outcomes is difficult to predict with available data.

[figure not shown]

Figure 7. Study power by effect size for the primary outcome (difference in estimated GFR in mL/min/1.73m 2).

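### The random-intercept primary model gives all eGFR changes one variance; if patients decline at different rates, the year-5 standard error may be too small

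*Combined protocol and SAP*

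**What the plan says.** The Protocol Addendum makes change in eGFR from baseline to year 5 the primary outcome (section 15b). Section 15e says: "The primary outcome is a continuous variable which will be tested using a linear mixed model with random intercepts". Equation 2 contains treatment, time, their product, a_i and e_ij. The terms are defined under Equation 1 in section 15d, where "a_i is a random effect for patient, and e is statistical error" and where j = 0, 2, 5 "represents the time period, t is time modeled categorically". Section 15e describes effects at years 2 and 5 but will "reserve statistical inference for year 5 alone".

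The same model is applied to "treatment effects on urine ACR, analyzed as a log-transformed continuous variable". Section 15c adds: "Multiple imputation for study participants missing year 5 eGFR will be conducted using chained equations"; it specifies no imputation of year-2 values. Sections 15c to 15g and D16 name no random slope, no other residual covariance, no robust variance and no sensitivity analysis of the covariance.

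**The concern.** A random intercept shifts a patient's whole trajectory up or down and cancels out of every within-patient change. What remains is the error, which on the usual reading is independent with constant variance. The model therefore imposes Var(Y2-Y0) = Var(Y5-Y2) = Var(Y5-Y0).

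In a progressive disease, patients may lose eGFR at different rates, or the within-patient correlation may fade with time. In either case, with similar residual variance at each visit, the longest interval has the largest change variance. Pooling it with the two shorter intervals makes the year-5 standard error too small. At stake are the primary confidence interval and p-value for each agent, both judged at 0.05. The condition is the same for log ACR, although the documents do not show whether log-ACR slopes vary.

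**Working it through.** **Inputs from the addendum.** Visits at years 0, 2 and 5; two-sided alpha 0.05; 80% power for a 2.3 mL/min/1.73m² difference; "1,058 participants (80%) contributing at least one follow-up blood sample", which is about 529 per arm for each factor.

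**The plan's own figure.** The 80% cannot be reproduced independently, because D16 refers to "variation in eGFR and its change over time as observed in the preliminary data from our study population" without giving an SD. Working backwards, and assuming that all 1,058 have a year-5 value, the implied SD of the 0-5 year change is 2.3 / (1.960 + 0.842) × √(529/2) = 13.35. The true year-5 SE is then 13.35 × √(2/529) = 0.821. This SD only sets the scale; the type I errors below do not depend on it.

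**Assumption.** The between-patient slope variance s² is not given. Let σ² be the residual variance at each visit, and let f be the share of the 0-5 year change variance due to true slope differences. The range of f is assumed.

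**Variances with linear slopes, complete data**
- 0-2 years: 2σ² + 4s²
- 2-5 years: 2σ² + 9s²
- 0-5 years (true): 2σ² + 25s²
- Used by the model, the average of the three: 2σ² + (4 + 9 + 25)s²/3 = 2σ² + 12.67s²

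With f = 25s²/(2σ² + 25s²), the ratio of model SE to true SE is r = √(1 − 0.493f), since (25 − 12.67)/25 = 0.493. Type I error is 2(1 − Φ(1.96r)).

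| f | Slope SD per year (at SD 13.35) | r | Model SE | Type I error |
|---|---|---|---|---|
| 0 | 0 | 1.000 | 0.821 | 5.0% |
| 0.10 | 0.84 | 0.975 | 0.800 | 5.6% |
| 0.25 | 1.34 | 0.936 | 0.769 | 6.7% |
| 0.50 | 1.89 | 0.868 | 0.713 | 8.9% |
| 0.75 | 2.31 | 0.794 | 0.652 | 12.0% |

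**Simulation.** With 529 per arm, complete data and 4,000 trials per setting, the random-intercept test rejected a true null in 5.1%, 5.2%, 7.0%, 8.6% and 11.4% of trials at these five values of f (Monte Carlo SE 0.3 to 0.5 points). Estimating the year-5 change variance directly gave 4.7% to 5.3%. A single fitted mixed model at f = 0.50 gave an SE of 0.712 against an empirical 0.818.

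**Imputation.** With ten imputations at f = 0.50, simulated type I error was 9.0% with 10% of year-5 values missing and 8.8% with 20% missing. The planned imputation does not repair the problem.

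**What shrinks or reverses the effect**
- *Missing year 2.* With a share m lacking year 2, the residual variance becomes [(1 − m) × average + m × V05/2] / [2(1 − m) + m], where V05 is the true 0-5 year change variance. At f = 0.10, 0.25, 0.50 and 0.75, type I error is 5.5%, 6.3%, 8.0% and 10.2% for m = 30%, and 5.4%, 6.0%, 7.3% and 8.9% for m = 50%.
- *Random-walk drift instead of linear slopes.* Change variance then grows in proportion to time, and r = √(1 − 0.333f). Type I error is 5.4%, 6.1%, 7.4% and 9.0% at the same f.
- *Noisier year 2.* The effect reverses once the year-2 residual variance exceeds that at years 0 and 5 by a factor above 1 + 18.5 s²/σ². That is 1.16, 1.49 and 2.48 at f = 0.10, 0.25 and 0.50.

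**The case against.** The strongest reply is that f is unknown. The documents give no slope SD, no visit-specific variances and no correlations across the three visits, so a possible weakness is shown, not an invalid test. Section VI.h of the original protocol also stresses large biological variation in single eGFR measurements, and such noise lowers f. At an SD of 13.35, f = 0.75 would need a single-visit noise SD of only 13.35 × √(0.25/2) = 4.7 mL/min/1.73m², which fits that description poorly. At low f, a modest excess of year-2 noise changes the direction. Finally, independent errors of constant variance are the usual reading of the model but are not stated, and the addendum refers to sections (D10, D12) that are not in the file.

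Most of this stands as a limit on size. The upper end of the range deserves less weight, and no single figure can be claimed. It does not remove the point. The protocol's own threshold for rapid loss in section VI.c is 3 mL/min per year and is said to predict mortality, which is hard to square with change being pure noise. A slope SD of 1.34 per year, under half that rate, already gives f = 0.25. If independent errors are not intended, the covariance behind the primary test is unspecified, and the same line of text settles it. The descriptive summary of 0-5 year change in section 15b might reveal a discrepancy but would not correct the planned p-value.

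**Conclusion.** The concern holds in its conditional form. If rates of decline differ between patients and residual variance is similar across visits, the planned year-5 SE is too small: by 2.5% at f = 0.10, 6.4% at f = 0.25 and 13% at f = 0.50. The nominal 5% test then runs at 5.6%, 6.7% or 8.9% with complete data, and somewhat less with year-2 gaps or random-walk drift. At f = 0 there is no problem. These figures rest on an assumed range for f and on the usual reading of the error term. Results near p = 0.05 are those most likely to be affected. The stated 80% power is neither confirmed nor refuted. This is a change that should be made, held with medium confidence.

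**What to change.** In sections 15d and 15e, replace the random intercept with an unstructured 3x3 within-patient covariance over years 0, 2 and 5, fitted by REML, for eGFR and for log ACR. Test the year-5 treatment-by-visit term from that model. A robust (sandwich) standard error would also protect the test. In D16, state which covariance the simulation generated and which model it fitted, and restate power if these differ from the final analysis.

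The cost is a line of text and six covariance parameters, which is no burden with about 1,058 participants. The downside is wider intervals if slopes vary, by the factor 1/r: about 3%, 7%, 15% and 26% at f = 0.10, 0.25, 0.50 and 0.75, and essentially no change at f = 0. If, and only if, the 80% in D16 came from data with varying slopes analysed by the random-intercept model, valid power at 2.3 is Φ(0.842 − 1.96(1 − r)), or 78.6%, 76.3% and 72.0% at f = 0.10, 0.25 and 0.50.

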IV.c. Treatment Assignment. Upon enrollment in the VITAL Diabetes ancillary study and/or parent VITAL trial, participants will be randomly assigned to vitamin D and omega-3 fatty acid treatment groups by the parent VITAL trial. Assignment to treatment groups will be accomplished using a computer-generated table of random numbers, stratified by 5-year age group. Within each age group, treatment assignments will be generated in blocks of eight individuals, with two individuals in each of the four treatment combinations: cholecalciferol + ω-3 FA, cholecalciferol + placebo, placebo + ω-3 FA, or placebo + placebo.

V. Study Procedures

V.a. Approach to Data Collection. We will collect all study data via mail, including questionnaires and urine and blood samples. The BWH Division of Preventive Medicine research group has extensive experience collecting and analyzing questionnaires and collecting, processing, and storing biospecimens using the mail-based collection procedures to be used in this study. We will utilize these established, standardized protocols, described below, for all data collection.

V.b. Questionnaire Data. All participants will be asked to complete diabetes questionnaires at baseline and after 4 years of study participation. Questionnaires will address diabetes diagnosis, diabetes history, history of kidney disease, and medication use related to diabetes and kidney disease.

V.c. Urine Collection. Each participant will be sent a standardized urine collection kit at baseline (pre-randomization) and again after 4 years of study participation. The kit will include instructions for proper collection of a clean-catch first morning void; a urine cup; a plastic single-use pipette; two 5-mL screw-top cryovials; a gel-filled freezer pack; and an overnight courier air bill. Participants will be instructed to fill each 5 mL cryovial with urine using the pipette, to securely close each cryovial, and to immediately mail both vials to the VITAL laboratory at the BWH Division of Preventive Medicine in the freezer packs provided. Upon receipt, any precipitate in the urine will be removed by centrifugation, and the urine will be aliquoted without preservative into six 2-ml Nunc vials. Urine samples will be thawed for measurements of albumin and creatinine.

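### After a non-significant interaction test, Equation 2 leaves out the other randomised agent; keeping both agents in one main-effects model is a free but very small gain in precision

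*Combined protocol and SAP*

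**What the plan says.** Section 15d of the addendum sets out Equation 1, a linear mixed model with vitamin D, omega-3, their product, and the products of each of these with time. A p-value below 0.05 for beta_6, the three-way term, "will be interpreted as evidence of interaction. If we observe interaction, all analyses will separately compare each of the 3 active treatment groups" with double placebo. Otherwise the comparison is made at the margins: "all participants assigned to any active vitamin D will be compared to all participants assigned to placebo vitamin D", and likewise for omega-3.

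For that second case, section 15e gives Equation 2, to test whether change in eGFR "differs by vitamin D treatment assignment in the absence of interaction with omega-3 fatty acids". It contains vitamin D, time, vitamin D by time and a random intercept, and no omega-3 term. The section then states: "Corresponding equations will test the effect of omega-3 treatment assignment on eGFR as well as treatment effects on urine ACR", the latter on the log scale. The plan will "reserve statistical inference for year 5 alone".

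No other section puts the second agent back. The extra terms foreseen in 15e are baseline characteristics found to be unbalanced (sensitivity analyses) and medication or laboratory covariates that diverge during follow-up (exploratory). Equations 3 and 4 in protocol section VI.e have the same one-agent form.

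On allocation, protocol section IV.c says: "Within each age group, treatment assignments will be generated in blocks of eight individuals", two to each of the four combinations. This applies to the parent trial. No stratification by diabetes or by sub-study membership is described.

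**The concern.** The step from Equation 1 to Equation 2 removes more than the test justifies. If beta_6 is not significant, the terms involving both agents together can reasonably go. The test says nothing about omega-3 or omega-3 by time, so the natural reduction is a main-effects model with both agents.

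Aims 1 and 2 hypothesise that each agent slows loss of GFR, and section D16 powers each for 2.3 mL/min/1.73m². If those hypotheses are right, each one-agent model leaves a real treatment effect in its residual. The parent trial's blocks do not force balance between the agents among sub-cohort members who return samples, so in the analysed set the agents are independent in expectation but not exactly balanced. What is at stake is the precision of each agent's year-5 estimate.

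**Working it through.** **Inputs**
- Analysed participants: 1,058, equal and independent allocation (section D16), so about 529 per level of each agent.
- Target difference 2.3 mL/min/1.73m² at year 5, two-sided alpha 0.05, power 80% (section D16).
- SD of change: not in the documents. Section D16 refers to a Section D12 that is not included.
- Effect g of the other agent on year-5 change: an assumption, taken from 0 to 5.

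**The plan's own figure.** Without an SD, the 80% cannot be reproduced from stated inputs. Solving for the SD that gives 80% power at 2.3 with 529 per level:
- SE = 2.3 / (1.960 + 0.842) = 0.821
- SD = 0.821 / sqrt(2/529) = about 13.35

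As a check on plausibility, protocol section VI.h gives SD 25 and correlation 0.834. The ANCOVA residual SD is 25 × sqrt(1 − 0.834²) = 13.79. With 600 per group this gives 70.9, 78.9, 85.4, 90.4, 94.0 and 96.5% for the six eGFR differences in Table 2, against stated values of 71, 79, 85, 90, 94 and 97%. The corresponding SD of a simple change is 25 × sqrt(2 × (1 − 0.834)) = 14.40. So 13.35 is reasonable but remains an assumption; a range of 10 to 18 is shown below.

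**Cost of omitting the other agent.** With half the participants on it, an agent with effect g adds g²/4 to the variance of change:
- SD_omit = sqrt(SD² + g²/4)
- For g = 2.3: sqrt(178.3 + 1.32) = 13.40, and 13.40 / 13.35 = 1.0037

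| Other agent's effect g | SD_omit | Increase in SE | Power, two agents | Power, Equation 2 form | Equivalent participants |
|---|---|---|---|---|---|
| 0 | 13.35 | 0% | 80.0% | 80.0% | 0 |
| 1.0 | 13.36 | 0.07% | 80.0% | 79.95% | 1.5 |
| 2.3 | 13.40 | 0.37% | 80.0% | 79.7% | 8 |
| 3.5 | 13.47 | 0.86% | 80.0% | 79.3% | 18 |
| 5.0 | 13.58 | 1.74% | 80.0% | 78.6% | 37 |

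Over SDs from 10 to 18, the loss of power is 0.2 to 0.3 points at g = 2.3 and 0.8 to 1.4 points at g = 5.

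**Chance imbalance.** The share on the other agent differs between arms with SD sqrt(0.25/529 + 0.25/529) = 0.0307. At g = 2.3 the estimate therefore shifts with SD 2.3 × 0.0307 = 0.07 mL/min/1.73m², about 9% of one SE (0.07 / 0.82). This is not a second loss:
- variance of the shift: g²/N = 5.29 / 1,058 = 0.0050
- increase in SE² from the residual: 4 × (g²/4) / N = 0.0050

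**Simulation.** 20,000 replicates per scenario, N = 1,058, unrestricted 1:1 randomisation of each agent, linear model on year-5 change, Equation 2 form against two-agent form:
- mean estimate 2.303 and 2.303 (both effects 2.3)
- power 79.9% and 80.2% (other effect 2.3); 78.5% and 79.6% (other effect 5)
- type I error 5.0% and 5.0% (other effect 2.3); 5.1% and 5.2% (other effect 5)
- coverage about 95% for both forms throughout
- when the other agent is inert, the two-agent SE is larger by about 0.05% (0.8215 against 0.8211)

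**The case against.** The best defence is that nothing here is an error. Equation 2 estimates the marginal contrast that 15d prespecifies. Recruitment to the sub-study takes place during the placebo run-in, before assignment (protocol sections III.c and IV), so imbalance between the agents at enrolment is pure chance. The simulation shows no bias, and valid tests and intervals. The loss at the design effect, 0.3 points of power, is also below the simulation error of the plan's own figure: with 2,000 replications, sqrt(0.8 × 0.2 / 2000) = 0.9 points. All of this stands. It limits the size of the point but does not remove it, because the two-agent model needs no new data and costs almost nothing.

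A reader might go further in three ways, none of them supported:
- That the omission biases the result or makes the test unreliable. Randomisation of both agents rules this out for the comparison as planned.
- That chance imbalance in the sub-cohort is a harm on top of the wider interval. It is the source of the extra variance, and Equation 2's standard error already reflects it.
- That the discrete Cox models for the categorical outcomes should change in the same way. The calculations cover only a linear model of change. In a hazard model, adding an effective agent also moves the target from a marginal to a conditional hazard ratio, so the change is not free in the same sense.

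**Conclusion.** The point holds as a free improvement of very small size. A non-significant beta_6 justifies dropping the vitamin D by omega-3 terms only, and Equation 2 and its counterparts drop the whole second agent. At the design effect of 2.3 mL/min/1.73m² for the other agent, the two-agent model is worth about 8 participants out of 1,058. No sample-size or inferential conclusion changes.

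The result rests on the back-solved SD, the assumed effect of the other agent, complete year-5 data, and a linear model of change, to which the random-intercept contrast reduces when data are complete and balanced. The simulation used unrestricted randomisation, so any balance carried over from the parent trial's blocks could only make the loss smaller. No separate figure was worked out for log urine ACR; the same reasoning applies because the model has the same linear form.

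**What to change.** State in 15e that, when the interaction is not retained, one model is fitted:

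eGFR_ij = b0 + b1(vitamin D_i) + b2(omega-3_i) + b3(t_ij) + b4(vitamin D_i × t_ij) + b5(omega-3_i × t_ij) + a_i + e_ij

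with time categorical, as in 15d. Both agents' year-5 effects are read from this model, and the same form is used for log urine ACR. The discrete Cox models are left as they are.

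The cost is one line in the analysis plan and a few degrees of freedom out of more than 1,000.

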Submitted in NIH grant renewal application 3/2/2015
Implemented upon funding 2/24/2016

15. Data analysis

15a. Descriptive analyses. We will describe creation of the VITAL diabetes sub-cohort according to CONSORT guidelines, including numbers of participants who consent to VITAL participation; report a diagnosis of diabetes; are approached for the DKD ancillary study; enroll in the DKD ancillary study; and complete year 2 and 5 year biosample collections. We will document reasons that participants do not complete the proposed studies. Among participants recruited into the DKD ancillary study, we will compare baseline characteristics of those who do and do not return at least one follow-up biosample collection. Among participants who return a follow-up biospecimen, we will describe by treatment assignment baseline characteristics and changes in clinical characteristics over the course of the study.

15b. Study outcomes. With an extension of follow-up from 2 to 5 years, we will have sufficient time to effectively evaluate change in estimated GFR (eGFR), a clinically relevant outcome.¹⁷⁵⁻¹⁷⁹ Therefore, if this competitive renewal is funded, change in eGFR from baseline to year 5 will supplant 2-year changes in albuminuria and eGFR as our primary study outcome. Change in eGFR will be calculated and summarized by treatment group as $[eGFR_5 - eGFR_0]$, where $eGFR_5$ represents eGFR at follow-up (year 5) and $eGFR_0$ represents eGFR at baseline. As secondary outcomes, we will examine changes in urine ACR from baseline to years 2 and 5, time to the development of rapid eGFR loss (loss of eGFR $\geq 40\%$ from baseline to year 2 or 5),¹⁷⁵⁻¹⁷⁹ and time to a composite of rapid eGFR loss, end stage renal disease (maintenance dialysis or kidney transplant verified by medical records review), or death. The composite outcome addresses large changes in eGFR which have particularly high clinical importance and reduces the potential impact of competing risks that preclude assessment of eGFR at follow-up.

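### The addendum's primary model tests year-5 change in eGFR without adjusting for baseline, which loses precision that data already in hand would supply

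*Combined protocol and SAP*

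**What the plan says.** Section 15b of the Protocol Addendum makes change in eGFR from baseline to year 5 the primary outcome: "Change in eGFR will be calculated and summarized by treatment group as" year-5 eGFR minus baseline eGFR. Section 15e says that it will be "tested using a linear mixed model with random intercepts". Equation 2 has a treatment main effect (beta_1), time, treatment by time (beta_3) and a random participant intercept. Section 15d defines the visits as 0, 2 and 5 and treats time as categorical.

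The coefficient of interest is described as follows: "where β_3 represents the difference in change in eGFR over time, comparing those on active vitamin D₃ to those on placebo". The plan continues: "The corresponding 95% confidence interval and p-value reflect statistical significance of the treatment effect". Both years are described, but the authors "reserve statistical inference for year 5 alone". Log ACR gets the same model.

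Baseline eGFR is therefore an outcome and not a covariate. The only planned baseline adjustment is conditional on imbalance: "sensitivity analyses will add to the model additional terms for such baseline characteristics". For missing data, section 15c says: "Multiple imputation for study participants missing year 5 eGFR will be conducted using chained equations". No imputation is stated for ACR.

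The original plan (section VI.e, Equations 3 and 4) used ANCOVA with the baseline value as covariate. The addendum gives no reason for dropping it.

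**The concern.** Baseline eGFR strongly predicts year-5 eGFR. Because beta_1 leaves the baseline mean free in each arm, Equation 2 uses the baseline value only by subtracting it. Subtraction is the best use of baseline only when the slope of follow-up on baseline is 1. Otherwise the primary test is less precise than it could be.

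A second question concerns validity. The confidence interval and p-value come from a covariance that pools one residual variance over visits 0, 2 and 5. That standard error is right for the year-5 contrast only under compound symmetry or a covariance that happens to give the same value. Whether the test holds its 5% level therefore depends on visit correlations that the documents do not give.

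**Working it through.** **Inputs.** From section VI.h: eGFR follow-up SD 25 and correlation with baseline 0.834; log ACR follow-up SD 1.59 and correlation 0.78. These come from outside cohorts and were used for a year-4 design. From D16: 1,058 participants (529 per arm), two-sided 0.05, 80% power for 2.3 mL/min/1.73m². Not in the documents, so assumed: the ratio k of baseline SD to follow-up SD, all year-2 correlations, and the addendum's own variance inputs (its Section D12).

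**The plan's own figures.** VI.h states 90% power with 600 per arm.
- eGFR: SD after ANCOVA is 25 × √(1 − 0.834²) = 13.79; power for 2.6 is 90.4%.
- Log ACR: 1.59 × √(1 − 0.78²) = 0.995; power for ln(0.83) is 90.0%.
- Raw change scores at k = 1 would give 87.8% and 86.4%, so the original figures rest on baseline adjustment.

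D16 cannot be reproduced. Its 80% at 2.3 implies an SD of 2.3 / (2.80 × √(2/529)) = 13.35 if all 1,058 have year-5 values. With the VI.h inputs, power would be 77.4% (ANCOVA) or 73.8% (change score, k = 1). D16 therefore does not reveal which model was simulated.

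**What Equation 2 estimates.** Under a random intercept, the difference between year 5 and baseline is uncorrelated with their sum and with year 2. With free means by arm and visit, the year-5 beta_3 is then the difference between arms in mean change. Fitting the model to simulated complete data agreed to within 2e-12.

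**Efficiency.** In units of the follow-up variance, with correlation r:
- change score: 1 + k² − 2rk
- baseline-adjusted: 1 − r²
- difference: (k − r)², which is never negative and is zero only when k = r (slope 1)

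The excess in true standard error is √[1 + (k − r)²/(1 − r²)] − 1.

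| k | eGFR (r = 0.834) | log ACR (r = 0.78) |
|---|---|---|
| 0.8 | 0.2% | 0.05% |
| 0.9 | 0.7% | 1.8% |
| 1.0 | 4.4% | 6.0% |
| 1.1 | 11.0% | 12.3% |
| 1.2 | 20.0% | 20.4% |

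For eGFR at k = 1 the variances are 0.332 and 0.3044. Their ratio is 1.0905, so Equation 2 would need 1,058 × 1.0905 = 1,154 participants to match the adjusted analysis.

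**Missing year-5 values (assumed 10% / 20%).** For eGFR imputed from arm, baseline and year 2, with all visit correlations 0.834, the excess is 4.1% / 3.7% at k = 1, 0.7% / 0.6% at k = 0.9 and 10.2% / 9.3% at k = 1.1. For log ACR without imputation, missing completely at random, with all correlations 0.78 and k = 1, it is 5.5% / 5.0%.

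**Conditional power.** Only if D16 was simulated under Equation 2, with a standard error equal to the true one, would adjustment raise 80% to 80.6%, 83.3% or 87.5% at k = 0.9, 1.0 or 1.1.

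**Reported against true standard error.** Take SD 25 at each visit, a baseline-to-year-5 correlation of 0.834 and complete data.
- True: √[2 × (625 + 625 − 2 × 0.834 × 625)/529] = 0.89.
- Reported: √(4s²/529), where s² = 625 × (1 − mean of the three visit correlations).
- Type I error: 2Φ(−1.96 × reported/true).

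| Correlation of year 2 with baseline and with year 5 (assumed) | Reported SE | Type I error | Simulated (10,000 trials) |
|---|---|---|---|
| 0.80 | 0.94 | 3.7% | 3.6% |
| 0.834 | 0.89 | 5.0% | 4.8% |
| 0.87 | 0.82 | 7.0% | 6.8% |
| 0.90 | 0.76 | 9.3% | 9.2% |

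Baseline ANCOVA stayed at 4.6% to 5.0% in the same simulations. With 10% to 20% of year-5 eGFR imputed (3,000 trials, 10 imputations), Equation 2 gave 3.8% to 9.5% and ANCOVA 4.7% to 5.8%.

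**The case against.** A longitudinal model of change is a recognised choice, matches an outcome defined as change, and is unbiased under randomisation. If D16 was simulated under Equation 2, the 2.3 mL/min/1.73m² target already includes any loss. The size of the loss is not a property of this trial: the correlations are borrowed, the SD ratio is assumed, and at a ratio of 0.9 the power gain is 0.6 points. The complete-data figures also slightly overstate a trial that expects missing year-5 samples. The covariance point runs from conservative to liberal, so its direction is unknown. Nor is the change wholly without consequence. With year-2 correlations of 0.90, nominal power for 2.3 is 82.0% under Equation 2 and 77.4% under adjustment.

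Most of this stands, and it is why the point is an improvement and not a correction. Three things remain.
- The direction of the efficiency result does not depend on the assumed inputs.
- The definition of the outcome is no obstacle: regressing year-5 eGFR, or its change, on arm and baseline gives the identical treatment coefficient.
- The 82.0% is obtained at a type I error of 9.3%, against 5% for the adjusted analysis, so the two powers are not comparable.

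Imputing from baseline does not help either, because the contrast fitted afterwards is still a change score.

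**Conclusion.** The point holds, as a matter to consider. Equation 2 gives an unbiased but less efficient year-5 contrast. At equal SDs the true standard error is about 4% too large for eGFR (4.4% with complete data, 3.7% with 20% imputed) and 5% to 6% too large for log ACR. It is close to zero when the SD ratio is near the correlation and about 11% to 12% at a ratio of 1.1. These sizes rest on the year-4 planning correlations and on assumed SD ratios. The stated 80% power is not shown to be wrong. The 5% level of the random-intercept test cannot be taken for granted, but the documents do not establish that it is inflated.

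**What to change.** In section 15e, make year-2 and year-5 eGFR the outcomes. Use visit, treatment by visit and baseline eGFR by visit as fixed effects, with an unstructured visit covariance, and test treatment at year 5. ANCOVA of year-5 eGFR on baseline in each imputed dataset is an equivalent route for eGFR. For log ACR use the mixed model: no ACR imputation is planned, so ANCOVA would be limited to complete cases. If a model with a common baseline mean is preferred, it also needs an unstructured covariance. The outcome definition in 15b can stay.

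The cost is analysis-plan wording, because baseline blood and urine are already required for entry. Record the change before unblinded year-5 results are examined, and state in D16 which model and visit covariance the power simulation used, re-running it if they differ from the revised test.
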